5.3 Treatment modification

Safety and tolerability of all patients will be closely monitored throughout study treatment and the follow-up period using the NCI CTCAE v.4.0.3. Patients will be assessed in order to detect any AEs before administering new study treatment during each treatment visit. Treatment will only be administered if clinical evaluation and local laboratory test results are acceptable.

If, in the opinion of the Investigator, a toxicity is considered to be due solely to one component of the study treatment (e.g., MK3475 (pembrolizumab) or eribulin) and the dose of that component is delayed or modified in accordance with the guidelines below, the other component may be administered if there is no contraindication. When treatment is temporarily interrupted because of toxicity caused by MK3475 (pembrolizumab) or eribulin, the treatment cycles will be restarted such that the MK3475 (pembrolizumab) and eribulin infusions remain synchronized. Patients who have both treatments withheld for more than 21 days must discontinue study treatment and are considered off study. Patients whose treatment is interrupted or permanently discontinued due to an AE, including abnormal laboratory value, must be followed until resolution or stabilization of the event, whichever comes first, which includes all study assessments appropriate to monitor the event.

5.3.1 Modification of the amount of study drug administered due to changes in patient's weight

MK3475 (pembrolizumab) is administered as a fixed dose irrespective of the patient's body weight.

The amount of eribulin is calculated according to the patient's body surface area (BSA). Weight and height should be recorded at baseline and the BSA calculated, thereafter at every scheduled visit for all patients should be re-weighed. The amount to be administered must be recalculated if the patient's body weight has changed by > 10% (increased or decreased) from baseline. Recalculation based upon smaller changes in body weight or BSA are at Investigators' discretion.

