5.3.2 Eribulin

Dose delay: The administration of eribulin should be delayed on day 1 or day 8 of each cycle for any of the following:

- ANC < $1 \times 10^9/L$ complicated or not by fever or infection.
- Platelets < $75 \times 10^9/L$.
- Grade 3 or 4 non-hematologic toxicities.

Retreatment following treatment interruption for toxicity may not occur until all of the following parameters have been met:

- ANC $\geq 1 \times 10^9/L$ and no fever.
- Platelets $\geq 75 \times 10^9/L$.
- Grade 3 or higher non-hematologic AEs have recovered to grade ≤ 1 or baseline (or, at the Investigator's discretion, grade ≤ 2 if not considered a safety risk for the patient).

Dose reduction: Dose reduction recommendations for eribulin retreatment are shown in the following tables.

Table 2. Eribulin dose adjustments for hematologic AEs

| Adverse reaction after previous eribulin administration | Recommended dose of eribulin |
|--|------------------------------|
| ANC < 0.5 x 10 ⁹ /L lasting more than 7 days | 0.97 mg/m ² |
| ANC < 1 x 10 ⁹ /L neutropenia complicated by fever or infection | |
| Platelets < 25 x 10 ⁹ /L | |
| Platelets < 50 x 10 ⁹ /L and complicated by haemorrhage or requiring platelet transfusion | |
| Reoccurrence of any hematologic adverse reactions as specified above | |
| Despite dose reduction to 0.97 mg/m ² | 0.62 mg/m ² |
| Despite dose reduction to 0.62 mg/m ² | Consider |

Absolute neutrophil count: ANC.

Table 3. Eribulin dose adjustments for non-hematologic AEs

| Adverse reaction after previous eribulin administration | Recommended dose of eribulin |
|---|------------------------------|
| Any grade 3 or 4 in the previous cycle | 0.97 mg/m ² |
| Reoccurrence of any non-hematologic adverse reactions as specified above | |
| Despite dose reduction to 0.97 mg/m ² | 0.62 mg/m ² |
| Despite dose reduction to 0.62 mg/m ² | Consider discontinuation |

Do not re-increase the dose of eribulin after it has been reduced.

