5.3.3 MK3475 (pembrolizumab)

AEs (both non-serious and serious) associated with MK3475 (pembrolizumab) exposure may represent an immunologic etiology. These AEs may occur shortly after study treatment initiation or several months after the last dose of treatment. MK3475 (pembrolizumab) must be withheld

for certain drug-related toxicities and severe or life-threatening AEs as per Table 4 below. Dose reduction of MK3475 (pembrolizumab) is not permitted.

MK3475 (pembrolizumab) should be permanently discontinued:

- For grade 4 toxicity except for endocrinopathies that are controlled with replacement hormones.
- If steroid dosing cannot be reduced to ≤ 10 mg prednisone or equivalent per day within 12 weeks.
- If a treatment-related toxicity does not resolve to grade 0-1 within 12 weeks after last dose of MK3475 (pembrolizumab).
- If any event occurs a second time at grade ≥ 3 severity (also for recurrent grade 2 pneumonitis).

Table 4. Dose Modification and Toxicity Management Guidelines for Immune-related AEs Associated with Pembrolizumab

| General instructions: | | | | |
|------------------------------|---|--------------------------------------|---|--|
| Immune-related AEs | Toxicity grade or condition (CTCAEv 4.0) | Action taken to pembrolizumab | irAE management with corticosteroid and/or other therapies | Monitor and follow-up |
| Pneumonitis | Grade 2 | Withhold | 
 • Administer corticosteroids (initial dose of 1-2 mg/kg prednisone or equivalent) followed by taper | 
 • Monitor participants for signs and symptoms of pneumonitis • Evaluate participants with suspected pneumonitis with radiographic imaging |
| | Grade 3 or 4, or | Permanently | | |

| | | | | |
|--|-------------------|---------------------------|---|--|
| | recurrent Grade 2 | discontinu e | | and initiate corticosteroid treatment 
 • Add prophylactic antibiotics for opportunistic infections |

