5.3.4 Supportive care guidelines for MK3475 (pembrolizumab)-related AEs

Pneumonitis: Steroids should be administered for grade ≥ 2 events (initial dose of 1-2 mg/kg/day prednisone or equivalent followed by a taper continued over no less than four weeks). MK3475 (pembrolizumab) should be withheld for grade 2 pneumonitis, and permanently discontinued for grade 3, grade 4, or recurrent grade 2 pneumonitis. Consider adding prophylactic antibiotics for opportunistic infections in the case of prolonged steroid administration.

Diarrhea/colitis: Subjects should be carefully monitored for signs and symptoms of enterocolitis such as diarrhea, abdominal pain, blood or mucus in stool, with or without fever. The potential risk of gastrointestinal perforation should be taken into consideration.

All subjects who experience diarrhea/colitis should be advised to drink liberal quantities of clear fluids. If sufficient oral fluid intake is not feasible, fluid and electrolytes should be substituted via IV infusion.

Steroids should be administered for grade ≥ 2 events (initial dose of 1-2 mg/kg/day prednisone or equivalent followed by a taper continued over no less than four weeks). MK3475 (pembrolizumab) should be withheld for grade 2 or 3 colitis, and permanently discontinued for grade 4 colitis.

T1DM (if new onset) or hyperglycemia: Insulin should be administered for T1DM and hyperglycemia, and MK3475 (pembrolizumab) should be withheld in cases of grade 3 or 4 hyperglycaemia until metabolic control is achieved. MK3475 (pembrolizumab) will be resumed when subjects are clinically and metabolically stable.

Hypophysitis: Steroids should be administered for grade ≥ 2 events (initial dose of 1-2 mg/kg/day prednisone or equivalent followed by a taper continued over no less than four weeks). Replacement of appropriate hormones should be administered as clinically indicated, and MK3475 (pembrolizumab) should be withheld for symptomatic hypophysitis until the event is controlled with hormone replacement.

Hepatotoxicity: Steroids should be administered [initial dose of 0.5-1 mg/kg/day (for grade 2 events) and 1-2 mg/kg/day (for grade 3 or 4 events) prednisone or equivalent followed by a taper continued over no less than four weeks]. MK3475 (pembrolizumab) should be withheld for grade

2 immune-related hepatitis, and permanently discontinued for grade 3 or 4 immune-related hepatitis.

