- Tumor burden remains $\geq 20\%$ and at least 5 mm absolute increase compared to nadir.
- Non-target disease resulting in initial disease progression is worse (qualitative assessment).
- New lesion resulting in initial disease progression is worse (qualitative assessment).
- Additional new lesion(s) since last evaluation.
- Additional new non-target progression since last evaluation.

If repeat imaging confirms disease progression due to any of the scenarios listed above, subjects will be discontinued from study therapy. If repeat imaging does not confirm disease progression by irRECIST and the subject continues to be clinically stable, treatment may continue and follow the regular imaging schedule.

*Note: If a subject with confirmed radiographic progression per irRECIST, but the subject is achieving a clinically meaningful benefit, and there is no further increase in the tumor burden at the confirmatory tumor imaging, an exception to continue treatment may be considered following consultation with the Sponsor. In this case, if treatment is continued, tumor imaging should continue to be performed following the intervals as outlined in **Appendix 1**.*

*Note: In subjects who discontinue study treatment without documented disease progression, every effort should be made to continue monitoring their disease status by tumor imaging following the intervals as outlined in **Appendix 1** until the start of new anti-cancer treatment, disease progression, death, or the end of the study, whichever occurs first.*

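### The 21-day combined-hold rule puts patients off study although other sections keep them in tumor and survival follow-up, and its relation to the 12-week pembrolizumab limit is unstated

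*Protocol*

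**What the plan says.** **Combined hold.** Protocol 5.3: "Patients who have both treatments withheld for more than 21 days must discontinue study treatment and are considered off study". The next sentence keeps adverse-event follow-up until the event resolves or stabilizes. It does not mention imaging or survival. The same section says that, for a toxicity due solely to one drug, "the other component may be administered if there is no contraindication".

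**Follow-up after stopping.** For patients who stop without progression, the closing note of Protocol 6.4.4 says "every effort should be made to continue monitoring their disease status by tumor imaging", and Appendix 1 footnote 4 repeats this. Sections 3.3.4 and 6.2 schedule a survival contact twelve months after the last dose. Sections 3.1 and 6.4.1, and the synopsis, list treatment discontinuation among the events that end scheduled tumor assessments.

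**Pembrolizumab limits.** Section 5.3.3 lists reasons for permanent discontinuation. One is a related toxicity not back to grade 0-1 twelve weeks after the last pembrolizumab dose. Another is "If steroid dosing cannot be reduced to ≤ 10 mg prednisone or equivalent per day within 12 weeks".

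**Events that can hold both drugs.** Section 5.3.2 delays eribulin for "Grade 3 or 4 non-hematologic toxicities". Section 5.3.4 says "MK3475 (pembrolizumab) should be withheld for grade 2 or 3 colitis, and permanently discontinued for grade 4 colitis".

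**The concern.** Leaving treatment and leaving the study are different events, and 5.3 merges them. A site that follows 5.3 to the letter would stop scans and survival contact for a patient whom 6.4.4, Appendix 1 and 6.2 still expect to follow. Sections 3.1 and 6.4.1 give that site further support for stopping the scans.

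The reason for the loss is treatment-related. Protocol 8.4 relies on dropout being unrelated to prognosis when it treats the Kaplan-Meier analyses as unaffected by withdrawal, and a toxicity-driven exit may not meet that condition. For the primary endpoint, the loss falls on patients whose benefit would have been stable disease lasting 24 weeks.

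There is a second, separate gap. One immune toxicity can hold both drugs, and the protocol then has two time limits without saying which governs or when the 21 days begin.

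**Working it through.** **1. Follow-up instructions side by side, for a patient stopped under 5.3 without progression**

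| Item | Ends it | Keeps it |
|---|---|---|
| Tumor imaging | 5.3 (off study); 3.1, 6.4.1 and synopsis (treatment discontinuation) | 6.4.4 note; Appendix 1 footnote 4 |
| Survival contact | 5.3 (off study) | 3.3.4; 6.2; Appendix 1 schedule |
| Adverse events | none | 5.3, next sentence |

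The conflict is therefore confined to imaging and survival.

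**2. Effect on each endpoint**

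- *CBR.* Protocol 8.2.1 and SAP 6.1.1 count complete response, partial response, or stable disease for at least 24 weeks. Scans are every 9 weeks, so 2 × 9 = 18 and 3 × 9 = 27: the first scheduled scan beyond week 24 is at week 27. A patient with stable disease at week 18 and no later scan has no scheduled evidence of 24 weeks. She stays in the full analysis set (Protocol 8.2.4, SAP 5) and counts as a non-responder (Protocol 8.4). The observed CBR can only fall. With 44 analysed, one such patient costs 1/44 = 2.3 points. A complete or partial response already documented is unaffected.
- *PFS.* SAP Appendix I, Tables 1 and 2, censor at the last assessment when treatment stops for toxicity. The off-study clause changes nothing here.
- *OS.* Protocol 6.4.3 and SAP Table 3 censor at last follow-up. If the contact is dropped, up to 12 months of survival information after the last dose is lost.

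**3. Scale for the primary test**

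The plan's own figure reproduces. For at least 17 of 39, the exact binomial gives one-sided alpha 0.04998 at a CBR of 30% and power 0.832 at 50%. The accrual target is 39/0.9 = 43.3, rounded up to 44.

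The documents give no rate for combined holds beyond 21 days. As an illustration only, let a share f of would-be benefit patients be counted as failures for this reason. The effective CBR is then 0.5 × (1 − f):

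| f (assumed) | Effective CBR | Power, ≥17/39 | Power, ≥19/44 |
|---|---|---|---|
| 0% | 50.0% | 83.2% | 85.4% |
| 2% | 49.0% | 79.8% | 82.2% |
| 5% | 47.5% | 74.1% | 76.5% |
| 10% | 45.0% | 63.0% | 65.1% |

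(19 is the exact cut-off with 44 analysed; alpha 0.0437.) At 50% of 44 there are 22 would-be benefit patients, so one lost patient corresponds to f = 1/22 = 4.5%. Only patients with stable disease and no earlier response can contribute to f.

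**4. The two time limits**

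The 12-week limit is 12 × 7 = 84 days, counted from the last pembrolizumab dose. The 21 days count time withheld, and no start is given. If withholding starts s days after the last pembrolizumab dose, the combined rule acts after day s + 21 and the gap is 84 − (s + 21).

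- s = 0: 84 − 21 = 63 days.
- s = 21 (the next cycle's dose is missed): 84 − 42 = 42 days.

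Grade 3 colitis shows that the overlap can occur: pembrolizumab is withheld (5.3.4, Table 4) and eribulin is delayed (5.3.2). The three-week limit at the end of 5.3.4 covers interruptions for reasons other than treatment-related events. SAP 5.1 puts interruptions over 21 days on the deviation review list. Neither settles precedence.

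**The case against.** The strongest reply is that the follow-up is already requested elsewhere, so off study can be read as off treatment. That is a sensible reading, and it makes the loss possible rather than certain. But it is not written down, and 3.1 and 6.4.1 point the other way on imaging.

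On the time limits, a reader might infer that 5.3 and 5.3.3 give opposite instructions. The documents do not support that. Section 5.3.3 lists triggers for stopping pembrolizumab for good and does not grant a 12-week hold, so a site that stops after 21 days of combined hold breaches nothing in it. The two limits could operate as whichever comes first, although the protocol does not say so.

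A reader might also infer that the steroid course, "followed by a taper continued over no less than four weeks", forces a combined hold past 21 days. It does not. Eribulin may restart under 5.3.2 once blood counts and toxicity have recovered (grade 1 or baseline, or grade 2 at the investigator's discretion), and no completed taper is required. The overlap is limited to events that keep eribulin on hold for more than 21 days.

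**Conclusion.** The off-study clause in 5.3 is inconsistent with the protocol's own imaging and survival follow-up and should be corrected. The possible loss is the 24-week stable-disease outcome and the survival contact. Its effect on CBR is conservative: 2.3 points per affected patient if 44 are analysed. The power illustration rests on an assumed f.

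Two stronger inferences fail. First, patients do not drop out of the CBR analysis: eligible treated patients remain in the full analysis set with missing counted as non-response. The contrast between 18/44 (p = 0.081) and 19/44 (p = 0.044) is arithmetically right, but it would apply to any single patient near the cut-off and does not measure this problem. Second, the clause does not bias PFS beyond what the SAP's censoring at a toxicity stop already does.

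What remains of the stopping-rule question is two limits, 42 to 63 days apart, with no stated precedence when both drugs are held for one toxicity. The sample size is not affected.

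**What to change.** 1. In 5.3, replace the off-study clause with a statement that the patient stops study treatment but remains in tumor and survival follow-up. Section 3.1 already uses this kind of wording for patients who complete 35 pembrolizumab doses.
2. Align the imaging stop rules in 3.1, 6.4.1 and the synopsis with 6.4.4 and Appendix 1 footnote 4. Changing 5.3 alone would leave this conflict in place.
3. Have the clinical team reconcile 5.3, 5.3.2 and 5.3.3: state which limit governs when both drugs are held for the same toxicity, and when the 21 days start. This review takes no view on which limit is right. SAP 5.1 should then match.

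The cost is a protocol clarification and continued follow-up of a few patients, most of it already requested. The PFS analysis would not change unless the SAP's censoring rules were also revised.

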5.3.2 Eribulin

Dose delay: The administration of eribulin should be delayed on day 1 or day 8 of each cycle for any of the following:

- ANC < $1 \times 10^9/L$ complicated or not by fever or infection.
- Platelets < $75 \times 10^9/L$.
- Grade 3 or 4 non-hematologic toxicities.

Retreatment following treatment interruption for toxicity may not occur until all of the following parameters have been met:

- ANC $\geq 1 \times 10^9/L$ and no fever.
- Platelets $\geq 75 \times 10^9/L$.
- Grade 3 or higher non-hematologic AEs have recovered to grade ≤ 1 or baseline (or, at the Investigator's discretion, grade ≤ 2 if not considered a safety risk for the patient).

Dose reduction: Dose reduction recommendations for eribulin retreatment are shown in the following tables.

Table 2. Eribulin dose adjustments for hematologic AEs

| Adverse reaction after previous eribulin administration | Recommended dose of eribulin |
|--|------------------------------|
| ANC < 0.5 x 10 ⁹ /L lasting more than 7 days | 0.97 mg/m ² |
| ANC < 1 x 10 ⁹ /L neutropenia complicated by fever or infection | |
| Platelets < 25 x 10 ⁹ /L | |
| Platelets < 50 x 10 ⁹ /L and complicated by haemorrhage or requiring platelet transfusion | |
| Reoccurrence of any hematologic adverse reactions as specified above | |
| Despite dose reduction to 0.97 mg/m ² | 0.62 mg/m ² |
| Despite dose reduction to 0.62 mg/m ² | Consider |

Absolute neutrophil count: ANC.

Table 3. Eribulin dose adjustments for non-hematologic AEs

| Adverse reaction after previous eribulin administration | Recommended dose of eribulin |
|---|------------------------------|
| Any grade 3 or 4 in the previous cycle | 0.97 mg/m ² |
| Reoccurrence of any non-hematologic adverse reactions as specified above | |
| Despite dose reduction to 0.97 mg/m ² | 0.62 mg/m ² |
| Despite dose reduction to 0.62 mg/m ² | Consider discontinuation |

Do not re-increase the dose of eribulin after it has been reduced.

5.3.3 MK3475 (pembrolizumab)

AEs (both non-serious and serious) associated with MK3475 (pembrolizumab) exposure may represent an immunologic etiology. These AEs may occur shortly after study treatment initiation or several months after the last dose of treatment. MK3475 (pembrolizumab) must be withheld

for certain drug-related toxicities and severe or life-threatening AEs as per Table 4 below. Dose reduction of MK3475 (pembrolizumab) is not permitted.

MK3475 (pembrolizumab) should be permanently discontinued:

- For grade 4 toxicity except for endocrinopathies that are controlled with replacement hormones.
- If steroid dosing cannot be reduced to ≤ 10 mg prednisone or equivalent per day within 12 weeks.
- If a treatment-related toxicity does not resolve to grade 0-1 within 12 weeks after last dose of MK3475 (pembrolizumab).
- If any event occurs a second time at grade ≥ 3 severity (also for recurrent grade 2 pneumonitis).

Table 4. Dose Modification and Toxicity Management Guidelines for Immune-related AEs Associated with Pembrolizumab

| General instructions: | | | | |
|------------------------------|---|--------------------------------------|---|--|
| Immune-related AEs | Toxicity grade or condition (CTCAEv 4.0) | Action taken to pembrolizumab | irAE management with corticosteroid and/or other therapies | Monitor and follow-up |
| Pneumonitis | Grade 2 | Withhold | 
 • Administer corticosteroids (initial dose of 1-2 mg/kg prednisone or equivalent) followed by taper | 
 • Monitor participants for signs and symptoms of pneumonitis • Evaluate participants with suspected pneumonitis with radiographic imaging |
| | Grade 3 or 4, or | Permanently | | |

| | | | | |
|--|-------------------|---------------------------|---|--|
| | recurrent Grade 2 | discontinu e | | and initiate corticosteroid treatment 
 • Add prophylactic antibiotics for opportunistic infections |
| Diarrhea / Colitis | Grade 2 or 3 | Withhold | 
 • Administer corticosteroids (initial dose of 1-2 mg/kg prednisone or equivalent) followed by taper | 
 • Monitor participants for signs and symptoms of enterocolitis (ie, diarrhea, abdominal pain, blood or mucus in stool with or without fever) and of bowel perforation (ie, peritoneal signs and ileus). • Participants with \geq Grade 2 diarrhea suspecting colitis should consider GI consultation and performing endoscopy to rule out colitis. • Participants with diarrhea/colitis should be advised to drink liberal quantities of clear fluids. If sufficient oral fluid intake is not feasible, fluid and electrolytes should be substituted via IV infusion. |
| | Grade 4 | Permanent ly discontinu e | | |
| AST / ALT elevation or Increased bilirubin | Grade 2 | Withhold | 
 • Administer corticosteroids (initial dose of 0.5-1 mg/kg prednisone or equivalent) followed by taper | 
 • Monitor with liver function tests (consider weekly or more frequently until liver enzyme value returned to baseline or is stable |
| | Grade 3 or 4 | Permanent ly discontinu e | 
 • Administer corticosteroids (initial dose of 1-2 mg/kg prednisone or equivalent) followed by taper | |

| | | | | |
|--|--|--|---|--|
| Type 1 diabetes mellitus (T1DM) or Hyperglycemia | Newly onset T1DM or Grade 3 or 4 hyperglycemia associated with evidence of β -cell failure | Withhold | 
 Initiate insulin replacement therapy for participants with T1DM Administer anti-hyperglycemic in participants with hyperglycemia | 
 Monitor participants for hyperglycemia or other signs and symptoms of diabetes. |
| Hypophysitis | Grade 2 | Withhold | 
 Administer corticosteroids and initiate hormonal replacements as clinically indicated. | 
 Monitor for signs and symptoms of hypophysitis (including hypopituitarism and adrenal insufficiency) |
| | Grade 3 or 4 | Withhold or permanently discontinue ¹ | | |
| Hyperthyroidism | Grade 2 | Continue | 
 Treat with non-selective beta-blockers (eg, propranolol) or thionamides as appropriate | 
 Monitor for signs and symptoms of thyroid disorders. |
| | Grade 3 or 4 | Withhold or permanently discontinue ¹ | | |
| Hypothyroidism | Grade 2-4 | Continue | 
 Initiate thyroid replacement hormones (eg, levothyroxine or liothyroinine) per standard of care | 
 Monitor for signs and symptoms of thyroid disorders. |
| Nephritis and Renal | Grade 2 | Withhold | 
 Administer corticosteroids (prednisone 1-2 mg/kg or equivalent) followed by taper. | 
 Monitor changes of renal function |
| | Grade 3 or 4 | Permanent ly | | |

| | | | | |
|------------------------------|--|--|---|--|
| dysfunction | | discontinu e | | |
| Myocarditis | Grade 1 or 2 | Withhold | 
 Based on severity of AE administer corticosteroids | 
 Ensure adequate evaluation to confirm etiology and/or exclude other causes |
| | Grade 3 or 4 | Permanent ly discontinu e | | |
| All other immune-related AEs | Intolerable / persistent Grade 2 | Withhold | 
 Based on type and severity of AE administer corticosteroids | 
 Ensure adequate evaluation to confirm etiology and/or exclude other causes |
| | Grade 3 | Withhold or discontinu e based on the type of event. Events that require discontinu ation include and not limited to: Gullain- Barre Syndrome, encephaliti s | | |
| | Grade 4 or recurrent Grade 3 | Permanent ly discontinu e | | |

1. Withhold or permanently discontinue pembrolizumab is at the discretion of the investigator or treating physician.

NOTE:

For participants with Grade 3 or 4 immune-related endocrinopathy where withhold of pembrolizumab is required, pembrolizumab may be resumed when AE resolves to ≤ Grade 2 and is controlled with hormonal replacement therapy or achieved metabolic control (in case of T1DM).

